9.3.2 ANALYSIS OF THE PRIMARY ENDPOINT(S)

Our primary outcome is biochemically confirmed alcohol abstinence, measured thrice daily throughout the 8-week study. Age and risky drinking will be determined based on self-report at the screening interview. Risky drinking will be defined using the AUDIT and AUD diagnosis will be confirmed by administering the DSM-5 checklist.²⁷ Research staff will also use this interview to assess for possible exclusionary cognitive or psychotic disorders using the MINI Neuropsychiatric Interview (M.I.N.I.). This variable will be analyzed as a repeated dichotomous variable.

If data are missing, missingness will be handled in a manner consistent with current expert recommendations, some of which have been established by our own team.^{20,22,24,38-43} Our approach emphasizes 1) either maximum likelihood or multiple imputations, and 2) extensive sensitivity analyses, including missing not at random approaches, to examine the robustness of treatment effects across varying assumptions. Maximum likelihood and multiple imputations have both shown exceptional performance compared to other, more common methods of handling missing data when the assumption of "missing at random" can be safely satisfied.³⁹

9.3.3 ANALYSIS OF THE SECONDARY ENDPOINT(S)

Secondary outcomes will include mobile usage, EMA bout completions, and self-reported alcohol use measured by the Timeline Follow Back²⁸ to assess the frequency and amount of daily drinking via multimodal EMA data collection by time, date and location. The Addiction Severity Index and quality of life in several domains (e.g., psychiatric, legal, medical) will be assessed at baseline.

9.3.4 SAFETY ANALYSES

Medical coding will use MedDRA for the concomitant diseases (Medical History) and AEs and the World Health Organization (WHO) Drug Dictionary for medications.

Each AE will be counted once only for a given participant. The AEs expectedness, severity, frequency, and their relationship to the study intervention will be presented by System Organ Class (SOC) and preferred term groupings. Adverse events leading to premature discontinuation from the study intervention and serious treatment-emergent AEs will be presented either in a table or a listing.

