1.2 SCHEDULE OF ACTIVITIES

Table 1. Schedule of study activities.

| | Baseline Week 0 | A-B-A Week 1-8 |
|--------------------------------------------------------------------|----------------------------|---------------------------|
| Informed consent | ✓ | |
| M.I.N.I*. Research Psychiatric Diagnosis | ✓ | |
| Medical history form | ✓ | |
| Other inclusion/exclusion criteria | ✓ | |
| Alcohol use (biochemical BAC **) | ✓ | 3x / day |
| Alcohol Timeline Follow Back (self-report) | ✓ | 3x / day |
| Addiction severity Index: ASI-Lite (self-report) | ✓ | |
| Alcohol cravings and withdrawal: visual analog scale (self-report) | ✓ | 3x / day |
| Location and Activity at time of the report | ✓ | 3x / day |
| Other substance use (biochemical) | ✓ | |
| Health-related quality of life (self-report) | ✓ | |
| Tobacco dependence (Fagerström***) | ✓ | |
| Alcohol dependence (AUDIT****) | ✓ | |
| Adverse Events | ✓ | weekly |
| Psychopathology (BSI*****) | ✓ | |
| Follow-up phone call | ✓ | weekly |
| Sleepiness Scale | ✓ | Weekly |

*The Mini-International Neuropsychiatric Interview (**M.I.N.I.**) is a short structured diagnostic interview, developed jointly by psychiatrists and clinicians.

**Blood Alcohol Concentration (BAC).

***The Fagerström Test for Nicotine Dependence is a standard instrument for assessing the intensity of physical addiction to nicotine.

****The Alcohol Use Disorders Identification Test (AUDIT).

*****The Brief Symptom Inventory (BSI).

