4 STUDY DESIGN

4.1 OVERALL DESIGN

This pilot study will utilize an A-B-A, completely within-subject design with the intent of recruiting twenty (n=20) total participants. During the first A phase, participants will receive reinforcement for simply submitting breath samples three times per day between 4 and 6 hours apart. In this application, we will utilize a Bluetooth enabled breathalyzer developed by BACtrack, but our smartphone-based technological solution will interact with any alcohol monitoring device, such as BACtrack Skyn. During the B phase, the delivery of reinforcers will be contingent upon the submission of an alcohol negative breath sample on an escalating schedule. The second A phase (i.e., return to the baseline phase) will involve the delivery of reinforcers for simply submitting a sample during the designated windows of time. We will also collect EMA data on stress, anxiety, depression, and other brief measures daily through their smartphone. Each phase will last a total of four weeks (i.e., two weeks of the first A phase, four weeks of the B phase, and then two more weeks of the A-phase) each for a total of 8 weeks of participation. To the extent possible, we will use existing protocols, procedures, and equipment that we have used in previous A-B-A studies.

This study will take place in Greater Inland Northwest area in cooperation with the Community Health Association of Spokane (CHAS) and other outpatient entities, community recruitment, etc. under the auspices of the WSU Program of Excellence in Addictions Research and the Analytics and PsychoPharmacology (APPL).

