8.3.3 CLASSIFICATION OF AN ADVERSE EVENT

8.3.3.1 SEVERITY OF EVENT

Each AE will be assigned a category by the Investigator as follows:

Mild: An AE that is easily tolerated by the subject, require minimal or no treatment and does not interfere with the participant's daily activities.

Moderate: An AE that results in a low level of inconvenience or concern with the therapeutic measures. Moderate events may cause some interference with functioning. Intervention may be needed.

Severe: An AE that prevents everyday activities and may require systemic drug therapy or other treatment. Severe events are usually potentially life-threatening or incapacitating.

If there is a change in the severity of an AE, it must be recorded as a separate event.

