8.3.5 ADVERSE EVENT REPORTING

Investigators must report to the IRB as soon as possible, but in all cases within seven (7) working days after the reportable event had been made known to the investigator. All AEs occurring during the study must be documented on the relevant CRF pages. The following information should be documented for each AE:

- Description of the symptom event
- Classification of "serious" or "not serious"
- Severity
- Date of first occurrence and date of resolution (if applicable)
- Action was taken
- Causal relationship
- The outcome of the event (unknown, recovered, not yet recovered, recovered with sequelae, death)

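### Section 9.3.4 counts each AE once per participant and tabulates without phase, a rule that fits a within-subject A-B-A design badly

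*Protocol*

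**What the plan says.** Section 9.3.4 gives the counting rule, "Each AE will be counted once only for a given participant", and the layout: expectedness, severity, frequency and relationship "will be presented by System Organ Class (SOC) and preferred term groupings". Neither sentence mentions phase. A separate table or listing is provided only for serious treatment-emergent AEs and AEs leading to discontinuation. Section 9.3.6 marks individual participant tabulation as not applicable.

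Section 4.1 describes a "completely within-subject design with the intent of recruiting twenty (n=20) total participants", with "two weeks of the first A phase, four weeks of the B phase, and then two more weeks of the A-phase".

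On recording, section 8.3.3.1 says "If there is a change in the severity of an AE, it must be recorded as a separate event". Section 8.3.5 asks for onset and resolution dates for every AE, and the schedule in section 1.2 has AEs collected weekly in weeks 1 to 8. Section 8.3.4 opens the recording window at consent and closes it 7 days (non-serious AEs) or 30 days (SAEs) after the last day of participation.

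**The concern.** Counting once per participant is a familiar convention in parallel-arm trials, where each person belongs to one arm. Here every participant passes through every condition, so a single count per person no longer belongs to one condition. If a participant has a headache in the first A phase and another in B, the literal rule counts one event, and B adds nothing to it.

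Phase matters for interpretation. Phase B is the one in which payment depends on alcohol-negative samples. The protocol treats withdrawal as a hazard: section 5.2 excludes people at significant risk of it, and section 8.3.3.3 gives expectedness to a provider with that expertise. Section 8.3.3.2 also uses timing to judge relatedness. For ordinary non-serious AEs, the table described in 9.3.4 is the only output the protocol names, and it does not show whether events fell in A or in B.

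**Working it through.** The protocol gives no AE rate, count or safety power, so there is no figure to reproduce. What follows is an illustration on assumed rates.

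**Inputs from the protocol:** 20 participants; phases of 2, 4 and 2 weeks (section 4.1), so 4 weeks in A and 4 weeks in B.

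**Assumed:** one preferred term with constant weekly rate λ in A and λr in B, the same for everyone, no carry-over and no withdrawals. λ runs from 0.05 to 0.4, and r = 2.

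**Step 1: the table as described.** The expected count is 20(1 − e^(−4λ−4λr)). With λ = 0.2 and r = 2 the exponent is 0.8 + 1.6 = 2.4, giving 18.2 of 20. A flat rate of 0.3 per week over 8 weeks also has exponent 2.4 and also gives 18.2. A doubling in B and no change in B therefore produce the same entry.

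**Step 2: if the single count were assigned to the phase of first occurrence** (a rule that the protocol does not state):

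- First A: 20(1 − e^(−2λ))
- B: 20 e^(−2λ)(1 − e^(−4λr))
- Second A: 20 e^(−2λ−4λr)(1 − e^(−2λ))

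For λ = 0.2, r = 2: first A = 20 × 0.3297 = 6.6; B = 20 × 0.6703 × 0.7981 = 10.7; second A = 20 × 0.1353 × 0.3297 = 0.9. The B/A ratio is 10.7/(6.6 + 0.9) = 1.43, against a true 2.

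**Step 3: once per participant per phase.** First and second A: 20(1 − e^(−2λ)) each. B: 20(1 − e^(−4λr)).

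**Step 4: all episodes.** 20 × 4λ in A and 20 × 4λr in B.

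Results for r = 2 (expected counts; triples are first A / B / second A):

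| λ per week | As described, no phase | First occurrence | B/A shown | Once per phase | Episodes A / B |
|---|---|---|---|---|---|
| 0.05 | 9.0 | 1.9 / 6.0 / 1.2 | 1.95 | 1.9 / 6.6 / 1.9 | 4.0 / 8.0 |
| 0.1 | 14.0 | 3.6 / 9.0 / 1.3 | 1.82 | 3.6 / 11.0 / 3.6 | 8.0 / 16.0 |
| 0.2 | 18.2 | 6.6 / 10.7 / 0.9 | 1.43 | 6.6 / 16.0 / 6.6 | 16.0 / 32.0 |
| 0.4 | 19.8 | 11.0 / 8.6 / 0.2 | 0.77 | 11.0 / 19.2 / 11.0 | 32.0 / 64.0 |

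Participants with the event in B but not counted there: 6.6 − 6.0 = 0.6 at λ = 0.05, and 16.0 − 10.7 = 5.3 at λ = 0.2. With no true phase effect (r = 1), first-occurrence assignment gives B/A ratios of 0.99, 0.96, 0.86 and 0.60 down the same four rates.

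**A limit of the once-per-phase count.** It restores the dropped participants and treats the two A phases alike, but it is still a count of people and saturates for frequent events. At λ = 0.2 its B/A ratio is 16.0/(6.6 + 6.6) = 1.21, further from 2 than 1.43. Only the episode count returns 2 (32.0/16.0). The gain is therefore completeness by phase, and participant counts should not be read as a rate ratio.

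**The case against.** The strongest reply is that nothing is lost and that the rest belongs in an SAP. Onset and resolution dates are recorded, AEs are collected weekly, and worsening gets its own record, so each event in weeks 1 to 8 can be placed in a phase. This stands: the limitation belongs to the described table and not to the data. Phase columns and the choice of severity are also commonly left to an SAP, which is not at hand, so their absence alone is no fault. What remains is that the protocol does state a counting rule, and an SAP that counted the same person's event again in B would depart from it as written.

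A second reply is that section 9.3.4 does not say whether an AE is a recorded event or a preferred term. If it is a recorded event, a recurrence with a new onset date could be counted in its own right, and only the missing phase dimension remains. Nor does the section state a time window; the whole-study window follows from a literal reading. Both points are fair.

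A third reply is proportion. This is a 20-person proof-of-concept trial with no safety endpoint and no planned comparison of AEs by phase, and section 2.3.1 describes the risk as negligible. At low rates the distortion is slight. This also stands.

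A reader might also infer that sections 8.3.3.1 and 9.3.4 conflict, since a change in severity creates a second record while the table counts once. They do not contradict each other: the first governs recording and the second counting, and both can be followed together.

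**Conclusion.** The point holds as a mismatch between a stated rule and the design. Read literally, section 9.3.4 drops recurrences in B of events first seen in the first A phase, and its table does not separate the two conditions. It is a cheap improvement of low severity. No primary-endpoint figure, alpha level or sample size is affected.

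The size depends on assumed rates and on a first-occurrence assignment that the protocol does not state. On those terms a true ratio of 2 appears as 1.95 at 0.05 per week, 1.43 at 0.2, and reverses to 0.77 at 0.4. For rare events the effect is negligible.

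Two stronger readings are tempting. One is that the trial cannot show a rise in events in phase B; the dated weekly records refute that. The other is that the rule makes later phases look safer; that would follow only if counts were assigned to the phase of first occurrence, and section 9.3.4 assigns them to no phase.

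**What to change.** In section 9.3.4, replace the counting sentence with wording to this effect:

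- Each preferred term is counted once per participant per phase (first A, B, second A) by onset date, at the worst severity in that phase.
- The denominator is the days actually observed in each phase, because participants may withdraw (section 7.1).
- Events between consent and the start of the first A phase, and events after the end of the second A phase, go in separate columns, since section 8.3.4 records both.
- An ongoing event that worsens is counted in the phase in which it worsens, using the separate severity records of section 8.3.3.1 linked to the parent event.

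Giving the number of episodes by phase beside the participant count would be sensible, because participant counts saturate for frequent events.

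The cost is about one paragraph of wording. The onset dates and severity records are already collected; the only addition is the link between a severity record and its parent event. The downside is a wider table with small cells at n=20.

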9.3.5 BASELINE DESCRIPTIVE STATISTICS

We will initially run descriptive statistics across baseline variables to characterize the sample. All inferential results will be presented as point estimates with 95% confidence intervals, and we will use an alpha error rate of 0.05 as the threshold for statistical significance. Our approach is consistent with that of several similar RCTs involving tobacco smoking and alcohol use disorders.^{12,13,24,34-37}

9.3.6 TABULATION OF INDIVIDUAL PARTICIPANT DATA

N/A

9.3.7 EXPLORATORY ANALYSES

N/A

10 SUPPORTING DOCUMENTATION AND OPERATIONAL CONSIDERATIONS

10.1 REGULATORY, ETHICAL, AND STUDY OVERSIGHT CONSIDERATIONS

Human subjects research at WSU is coordinated through the WSU Institutional Review Board (IRB). The IRB is responsible for the review and approval of all research activities involving human subjects. The IRB is charged with protecting the rights and welfare of human subjects to ensure that all study participants are treated physically, psychologically, and socially in such a way as to minimize embarrassment and stress and to avoid harm or other negative effects.

All Research staff will complete online training through the Collaborative Institutional Training Initiative (CITI) <https://about.citiprogram.org/en/homepage/>, a web-based training program on Human Research Subject protections, before starting the study training.

All Research Coordinators and Research Associates will complete all the following before interacting with participants:

Thoroughly read the protocol and guidelines on consenting and safety procedures found below. Research Coordinator should be knowledgeable on all procedures and safety procedures. This includes HIPAA training. Documentation of course completion will be included in the study file.

Practice all study procedures & consenting with existing study personnel. All study staff should be able to answer frequent questions from participants.

Shadow and watch an approved Research Coordinator complete an entire study visit: recruiting, consenting, and enrolling a participant.

Receive approval by the Principal Investigator to conduct the consenting.

10.1.1 INFORMED CONSENT PROCESS

The process of obtaining informed consent is a basic ethical obligation and a required element of a human subject's research. The IRB will require that informed consent be documented using a written consent form approved by the IRB and signed and dated by the subject. The participant will be given ample time to read the consent document before it is signed. A copy of the document will be given to the person signing the form.

The informed consent form will be presented to allow potential participants to review facts about the study and what will be asked of them so that they can voluntarily choose whether to participate as a research subject.

Changes to the study protocol may result in the need for a new consent form. Only the current approved consent form will be used. The consent form document will have an IRB stamp of approval, version number, and date at the bottom of each page.

Please note: Unless you have the PI's authorization, do not conduct the consenting process.

10.1.1.1 CONSENT AND OTHER INFORMATIONAL DOCUMENTS PROVIDED TO PARTICIPANTS

Consent forms describing in detail the study procedures, and risks will be given to the participant and written documentation of informed consent will be completed before starting the study. The following consent materials are submitted with this protocol:

- 1- Printed written consent form
- 2- Web-based consent with an electronic signature
- 3- HIPAA Authorization form

10.1.1.2 CONSENT PROCEDURES AND DOCUMENTATION

The consenting process will be conducted consistently for every participant.

If a participant is eligible, the iPad that was used for screening will display the consent form. The research assistant (RA) or research coordinator (RC) will explain that this document will explain the details of the study they are being asked to take part in. Allow the participant plenty of time to read.

When the participant is done reading the consent, they will be asked if they have any questions about the study. If the answer to a question is not immediately obvious, the research coordinator or an investigator will be asked for their opinion, which must also be documented. The consent form will then be thoroughly reviewed to ensure that the participant understands what they are agreeing to.

Eligibility for the study is determined by study procedures. Signing the consent does not ensure eligibility to participate. That said, it will be made clear to the prospective participant that participation will not impact their care.

The key point to stress in the consenting process is that **PARTICIPATION IS VOLUNTARY**. Participants can choose not to consent to the study or discontinue at any time for any reason. They can choose not to answer any questions that make them feel uncomfortable.

The RA/RC will show the participant where to type their name and date the consent form. The participant must date and place their signature or initials on consent. The RA/RC will give a paper copy of the consent to the participant for their records.

Remember that consenting is an ongoing process.

10.1.2 STUDY DISCONTINUATION AND CLOSURE

This study may be suspended or prematurely terminated if there is sufficient reasonable cause. Written notification, documenting the reason for study suspension or termination, will be provided by the suspending, or terminating party to study participants, investigators, funding agencies, and regulatory authorities. If the study is prematurely terminated or suspended, the Principal Investigator (PI) will promptly inform study participants, the Institutional Review Board (IRB), and sponsor/funding agency and will provide the reason(s) for the termination or suspension. Study participants will be contacted, as applicable, and be informed of changes to the study visit schedule.

Circumstances that may warrant termination or suspension include, but are not limited to:

- Determination of unexpected, significant, or unacceptable risk to participants.
- Demonstration of efficacy that would warrant stopping.
- Insufficient compliance with protocol requirements.
- Data that are not sufficiently complete and/or evaluable.
- The determination that the primary endpoint has been met.
- Determination of futility.

The study may resume once concerns about safety, protocol compliance, and data quality are addressed, and satisfy the funding agency, sponsor, IRB, or other relevant regulatory or oversight bodies.

10.1.3 CONFIDENTIALITY AND PRIVACY

The risk to patients from digital intervention is negligible. All data is collected in a HIPAA-compliant manner. Private identifiable information will be encrypted and kept secure. A research coordinator who has been trained in the proper performance of these duties will obtain informed consent.

Study visits will be conducted in a manner to protect participant privacy. The consent process, administration of questionnaires, assessment and biologic sampling, medication dispensing, and CM draws will occur in a restricted area. To reduce the risk of unauthorized disclosure of confidential information all personal identifiers will be kept separate from participant files and a study-specific research identification number (key) will be assigned to each participant. Data will be collected, entered, and accessed by study personnel trained in issues of confidentiality related to human subject protection. The key will be kept separate and not in the same enclave component of the network. Data will be entered into a password-protected database that is encrypted and firewalled. All information provided by the participant will be kept private except in the case that this would immediately put the participant or someone else in danger. In that case, the Investigator would release information to keep the participant or another person safe. If the investigator learns about abuse to a child or an elder, that information must be reported to the proper authorities.

10.1.4 FUTURE USE OF STORED SPECIMENS AND DATA

No specimens will be stored for this study. All paper records be shredded, physical tapes are erased, and physically destroyed, and electronic media be scrubbed after the files are deleted. (Entirely de-identified data where all links to individual identity including any information that could identify participants will be retained.) See: WSU BPPM 90.01 - <https://policies.wsu.edu/prf/index/manuals/90-00-records/90-01-research-sponsored-project-records/>

All research materials (consent forms, surveys, digital) will be kept for a minimum of three years after completion of the study. See: WSU BPPM 90.01 - <https://policies.wsu.edu/prf/index/manuals/90-00-records/90-01-research-sponsored-project-records/>

